8.7 Pharmacodynamics

Pharmacodynamic parameters will not be evaluated in this study.

8.8 Biomarkers

Collection of samples for other biomarker research is also part of this study. The following samples for biomarker research are required and will be collected from all participants as specified in the SoA:

- Blood for planned genetic analysis.

8.8.1 Planned Genetic Analysis Sample Collection

The planned genetic analysis sample should be drawn for planned analysis of the association between genetic variants in DNA and drug response. This sample will not be collected at the site if there is either a local law or regulation prohibiting collection, or if the IRB/IEC does not approve the collection of the sample for these purposes. If the sample is collected, leftover extracted DNA will be stored for FBR if the participant provides documented informed consent for FBR. If the planned genetic analysis is not approved, but FBR is approved and consent is given, this sample will be collected for the purpose of FBR.

The planned genetic analysis sample should be obtained pre-dose on Day 1 but may be collected at the next scheduled blood draw, if needed. Sample collection, storage, and shipment instructions for planned genetic analysis samples will be in the Operations/Laboratory Manual.

8.9 Future Biomedical Research Sample Collection

If the participant provides documented informed consent for FBR, the following specimens will be obtained as part of FBR:

- Leftover specimens listed in Section 8.8.

8.10 Medical Resource Utilization and Health Economics

Medical Resource Utilization and Health Economics are not evaluated in this study

8.11 Visit Requirements

Visit requirements are outlined in Section 1.3. Specific procedure-related details are provided in Section 8.

8.11.1 Screening/Rescreening

Approximately 45 days before intervention randomization, potential participants will be evaluated to determine that they fulfill the entry requirements as set forth in Section 5.

8.11.1.1 Screening

The screening window, which is a \leq 45-day window prior to randomization, will begin on the date of the documented main study consent for the participant. During the screening window, potential participants will be evaluated to determine that they fulfill the entry requirements as set forth in Section 5. Select screening procedures may be repeated after consultation with the Sponsor. If a participant has passed the 45-day screening window, the participant may be allowed to rescreen.

8.11.1.2 Rescreening

If the 45-day screening window has been exceeded, participants are allowed to rescreen 1 time. Once a participant has started the rescreening process, a new screening period (ie, an additional \leq 45-day window) will begin, during which time screening procedures may be repeated and are expected to be completed within this new 45-day window.

Documented informed consent (for the main study, FBR [if applicable], PBMC Subset [if applicable] and all other locally applicable study consent forms [eg, Greenphire]) obtained during the original screening period should be reviewed with the participant, including any screening procedures that need to be repeated, and a verbal reconsent to continue in the study should be documented.

Evaluation of eligibility will be determined through repeating select screening procedures during the rescreening process to ensure that participants are still at low-risk for HIV-1 infection and in generally good health, as outlined below. If a procedure is required to be repeated at rescreening, that result will be used to confirm eligibility.

All Participants

The following assessments must be repeated for all participants during rescreening:

- Register the rescreening in the IRT system
- Review medical history, HIV infection risk, prior/concomitant medications use, and contraceptive use
- Review AEs
- 12-lead ECG
- Complete physical examination
- Complete set of vital signs, including height and weight
- HIV-1 and HIV-2 testing
- HBV and HCV testing
- Serum pregnancy test
- Hematology, chemistry, CrCl, cystatin-C, TBNK Panel, and PT/INR

The following assessments do not need to be repeated at rescreening if the participant had a negative test result at the original screening visit, ≤ 60 days have passed since the date of the original sample collection, and the participant does not report an increase in risk for HIV infection; however, testing must be performed at rescreening if any of the above criteria are not met:

- Syphilis serologic testing
- Urine GC/CT & trichomoniasis testing (females only)
- Urine GC/CT testing (males only)

8.11.2 Intervention Period

During the intervention period, participants will receive a total of 6 oral doses of the assigned blinded study intervention (MK-8527 [3 mg, 6 mg, or 12 mg] or placebo) per the SoA. Administration of study intervention will be witnessed by the investigator and/or study staff approximately every 4 weeks starting on Day 1. The final dose will be administered at the Week 20 visit.

After Day 2, participants in the PBMC Subset will return to the site at Weeks 1, 2, and 3 for additional required assessments, per the SoA (Section 1.3.1).

8.11.2.1 AE Assessment Phone Call (Week 2)

A phone call to collect safety information will be made at Week 2 for participants not in the PBMC Subset. The investigator is responsible for ensuring that all telephone contacts are performed by a staff member who is a health care professional qualified to elicit a discussion with the participant that will lead to a clinically meaningful disclosure on the participant's well-being. Telephone contacts are to be documented in the source documents and in the EDC tool (if required) and the investigator must review the entry within 2 days. However, if the participant reports any clinically concerning events (eg, SAEs, ECIs) during a telephone call, then the investigator must be promptly notified. The investigator will contact the participant to determine if a clinic visit is warranted.

If the participant cannot be reached by telephone at the regularly scheduled time, the site should make at least 3 attempts (in addition to the initial phone call) to contact the participant within 48 hours of the missed scheduled time. The participant's reliable contact person should be called if attempts to contact the participant are not successful. All phone contacts and attempts should be recorded in source documents.

8.11.3 Participants Discontinued From Study Intervention but Continuing to be Monitored in the Study

Participants who discontinue study intervention before the final dose at Week 20 should complete an EOT visit (Visit 11) (Section 1.3.1), and then continue with the protocol-specified visits for the "Follow-up (Blinded)" study period as listed in the SoA (Section 1.3.1) and further described in Section 8.11.6.

For the EOT visit, the site should perform all procedures, as listed in the SoA (Section 1.3.1) for Visit 11 (Week 20/EOT), except for the following procedure modifications:

1. No study intervention should be dispensed via the IRT or administered to the participant. The site should call the IRT to register the EOT visit.
2. One sample for plasma MK-8527 PK collected, at any time during the visit.
3. If in the PBMC Subset: only 1 PBMC sample and 1 VAMS venous sample should be collected, at any time during the visit.

If a participant discontinues study intervention before the final dose at Week 20, the EOT visit (Visit 11) should be performed in place of the next study visit. If a participant discontinues study intervention and also withdraws from the study before the final dose at Week 20, then only the EOT visit (Visit 11) should be performed in place of the next study visit. If a participant receives the final Week 20 dose of study intervention and then withdraws from the study, an “Early Withdrawal From Study” visit should be performed as the final study visit as outlined in Section 1.3.2 of the SoA.

8.11.3.1 Management of Participants with Specified Decreases in Total Lymphocyte Count or CD4+ T-cell Counts

Participants discontinued from study intervention (prior to the final dose at Week 20) due to confirmed decreases in total lymphocyte count or CD4+ T-cell count (Section 7.1 and [Table 3](#)) should undergo assessments for the EOT visit (Visit 11) as specified in the SoA in Section 1.3.1. To meet the protocol-defined discontinuation criteria, participants must have a confirmed total lymphocyte count or CD4+ T-cell count that indicates a specified decrease on 2 consecutive measurements 1 to 4 weeks apart ([Table 3](#)). Note: The time frame for confirmation of decreases in total lymphocyte count or CD4+ T-cell count may be extended in the setting of intercurrent illness, immunization, or study intervention dosing interruptions (due to missed study visits). Allow approximately 4 weeks following resolution of illness, immunization, or study intervention dosing interruptions before collecting the confirmation sample to allow for evaluation of a potential other causal effect. Consult with the Sponsor prior to discontinuation if the investigator believes there is an alternative explanation for the result (eg, COVID-19).

After discontinuation from study intervention, participants should continue to be followed in the study, by completing the follow-up visits as outlined in the SoA in Section 1.3.1.

Total lymphocyte counts and CD4+ T-cell counts will also be monitored during follow-up (after last dose at Week 20). If a participant has a confirmed decrease in total lymphocyte count or CD4+ T-cell count as per Section 7.1, [Table 3](#), after the last dose at Week 20, participants should continue to be followed in the study, by completing the follow-up visits as outlined in the SoA in Section 1.3.1.

If at the Follow-up Week 8 visit the participants total lymphocyte count and/or CD4+ T-cell count has not returned to ≥ 1000 cells/mm³ or ≥ 500 cells/mm³, respectively, on 2 consecutive measurements, the participants should continue to be followed in the study with approximately monthly unscheduled visits. At the unscheduled visit, the site should complete

an AE assessment and collect hematology and TBNK Panel/CD4+ T-cell samples for evaluation by the central laboratory. Participants should continue with the unscheduled visits until the total lymphocyte count and/or CD4+ T-cell count has returned to ≥ 1000 cells/mm 3 or ≥ 500 cells/mm 3 , respectively, on 2 consecutive measurements.

8.11.3.2 Participants Who Become Pregnant

If a participant becomes pregnant prior to the last dose of study intervention at Week 20, an EOT visit (Visit 11) as per the SoA in Section 1.3.1 should be performed. If the pregnancy is reported at a scheduled study visit (eg, Week 8), the assessments/procedures for the EOT visit (Visit 11) should be conducted at that time. The participant will then continue with the protocol-specified visits for the “Follow-up (Blinded)” study period (Follow-up Day 1, Follow-up Week 4, etc) as listed in the SoA in Section 1.3.1.

If the participant becomes pregnant after the last dose of study intervention at Week 20 or during the “Follow-up (Blinded)” study period they should continue with the protocol-specified follow-up visits listed for this period in the SoA in Section 1.3.1.

All reported pregnancies will be followed to the completion/termination of the pregnancy (Section 8.4.5).

8.11.4 HIV Infection Confirmation

Participants who have a positive HIV-1/2 screen test should return to the site for an “HIV Infection Confirmation” visit within 14 days of the site receiving the positive test result and have procedures performed as specified in the SoA in Section 1.3.2, including collection of an HIV-1 RNA PCR sample.

- If the positive HIV-1/2 screen test is prior to the last dose of study intervention at Week 20, and the HIV confirmation and differentiation test is negative, the participant may continue study intervention while waiting for the results of the HIV-1 RNA PCR test.
 - If the HIV-1 RNA PCR test is negative, the participant can continue to take study intervention.
 - If the HIV-1 RNA PCR test is positive, the participant should complete an EOT visit (Visit 11), and then continue with the protocol-specified visits for the “Follow-up (Blinded)” study period as listed in the SoA in Section 1.3.1. The participant should be referred to local medical providers for HIV care and treatment. No poststudy ART will be provided by the study.
- If the positive HIV-1/2 screen test is prior to the last dose of study intervention at Week 20, and the HIV confirmation and differentiation test is positive, the participant should **not** receive additional doses of study intervention while waiting for the results of the HIV-1 RNA PCR test.
 - If the HIV-1 RNA PCR test is negative, the participant may be able to resume study intervention after consultation with the Sponsor.

- If the HIV-1 RNA PCR test is positive, the participant should be permanently discontinued from study intervention and complete an EOT visit (Visit 11), and then continue with the protocol-specified visits for the “Follow-up (Blinded)” study period as listed in the SoA in Section 1.3.1. The participant should be referred to local medical providers for HIV care and treatment. No poststudy ART will be provided by the study.
- If the positive HIV-1/2 screen test is after the last dose of study intervention at Week 20 or during the “Follow-up (Blinded)” study period, the participant should continue with the protocol-specified visits listed for this period in the SoA in Section 1.3.1.
- The study investigator should utilize the results of the HIV confirmation and differentiation test and HIV-1 RNA PCR to determine the appropriate follow-up care for the participant.

If a participant has repeated positive HIV-1/2 screening tests which the investigator considers to be false positive results (due to the biology of the participant), after consultation between the site and the Sponsor, and written documentation of the collaborative decision, HIV RNA testing can be performed at each scheduled visits to avoid the participant needing to return for an HIV confirmation visit with each false positive screening test result.

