1.3.2 Schedule of Activities (HIV Infection Confirmation or Early Withdrawal From Study)

Study Period	HIV Infection Confirmation ^a	Early Withdrawal From Study ^b	Notes
Visit Number	Unscheduled		
Scheduled Day/Week	HIV Infection Confirmation	Early Withdrawal From Study	
Visit Window	Within 14 days of HIV-positive test	NA	
Administrative Procedures			
Offer condoms and lubricant	X		For sexually active participants. Document in participant chart.
Register study visit in IRT		X	
Safety Procedures			
HIV infection risk evaluation	X	X	Document in participant chart. Assess any changes in risk status and PrEP eligibility (Appendix 8).
Concomitant medication review	X	X	
Contraceptive use confirmation (POCBP only)	X	X	Document in participant chart.
Symptom-directed physical exam		X	
Vital signs		X	Includes body temperature, pulse, respiratory rate, and systolic and diastolic blood pressure
Weight		X	
AE assessment	X	X	
12-lead ECG		X	Only perform at the Early Withdrawal visit if the participant discontinues prior to the Week 20 ECG collection.
Laboratory Evaluations/Procedures			
HIV-1 and HIV-2 screen		X	
HIV-1 RNA PCR	X		
HIV-1 drug resistance testing	X		
Urine pregnancy test (POCBP only)		X	Conduct per local regulations. Positive results to be confirmed with serum pregnancy test.
Hematology	X	X	
TBNK Panel/CD4+ T-cell count	X	X	
Chemistry		X	
Creatinine clearance calculation (CG)		X	
Cystatin-C		X	
Pharmacokinetics (All participants)			
Plasma PK sample collection	X	X	Not required if participant is beyond Follow-up Day 1.

Study Period	HIV Infection Confirmation ^a	Early Withdrawal From Study ^b	Notes
Visit Number	Unscheduled		
Scheduled Day/Week	HIV Infection Confirmation	Early Withdrawal From Study	
Visit Window	Within 14 days of HIV-positive test	NA	
Pharmacokinetics (PBMC Subset)			Participants are from preselected sites. Refer to laboratory/study operation manual for special collection and processing requirements.
PBMC collection	X	X	
Venous microsampling (eg, Mitra [®] /VAMS)	X	X	

AE=adverse event; CG=Cockcroft-Gault; ECG=electrocardiogram; HIV=human immunodeficiency virus; IRT=Interactive Response Technology; PBMC=peripheral blood mononuclear cells; PCR=polymerase chain reaction; PK=pharmacokinetic; POCBP=participants of childbearing potential; PrEP=pre-exposure prophylaxis; RNA=ribonucleic acid; TBNK=T- and B-lymphocyte natural killer cell; VAMS=volumetric absorptive microsampling.

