Note: If a participant has a change in HIV-1-associated risk behavior (Appendix 8), he/she may become eligible to receive a medication approved PrEP (eg, FTC/TDF, FTC/TAF, or cabotegravir IM), and discontinuation from study intervention may be indicated. The investigator should discuss any changes in HIV-1-associated risk behavior with the Sponsor's Clinical Director. The decision to continue the participant on study intervention or discontinue the participant with referral to locally available HIV prevention services, including services for approved PrEP, will be determined by agreement between the investigator and the Sponsor.

Note: If a participant requires PEP for potential occupational or non-occupational HIV exposure, the decision to continue the participant on study intervention or discontinue the participant will be determined by agreement between the investigator and the Sponsor.

- The participant has a confirmed positive serum pregnancy test.
- The participant develops a malignancy after randomization.

- The participant has confirmed HIV-1 or HIV-2 infection.

Note: Participants who become infected with HIV-1 or HIV-2 prior to Follow-up Week 8 may have their treatment unblinded.

Note: Participants who become infected with HIV-1 or HIV-2 during the study will stop receiving study intervention and will be referred to local medical providers for HIV care and treatment. No poststudy ART will be provided by the study.

- The participant has an SAE or Grade 4 laboratory AE assessed by the investigator to be related to study intervention AND that is life-threatening or results in prolonged hospitalization.
- A participant must be discontinued from study intervention and managed per Section 8.11.3.1 if any of the criteria in **Table 3** are confirmed. Participants should interrupt QM blinded dosing pending confirmatory testing.

Note: If the investigator believes there is an alternative explanation for the result (eg, COVID-19), consultation between the investigator and Sponsor is required when evaluating the participant for discontinuation from study intervention.

Table 3 Discontinuation Criteria for Specified Decreases in Total Lymphocyte Counts or CD4+ T-cell Counts

Laboratory Test	Criterion ^a	Confirmation ^{b,c}
Total lymphocyte count	A confirmed on-treatment value <1000 cells/mm ³ with a ≥30% decline from baseline	Repeat measurement 1 to 4 weeks later or at the next scheduled study visit, whichever is sooner

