8.3.2 Vital Signs

Vital signs will be measured after approximately 5 to 10 minutes of rest and will include temperature, pulse, respiratory rate, and systolic and diastolic blood pressure.

Note: Oral temperatures should be taken. If an oral temperature measurement is not possible, a temporal, tympanic, rectal, or axillary temperature measurement may be taken and should be recorded appropriately.

8.3.3 *Electrocardiogram*

Procedures for printing, archiving, and review of ECGs will be specified by the central vendor.

Sites will receive an immediate, machine-read QTcF value when the ECG is performed using the central vendor supplied machine. This value may change on the final cardiologist-read ECG report; therefore, sites should use only the final ECG report QTcF value from the screening visit to determine participant eligibility.

In some instances, the Sponsor may request that the site do a repeat ECG to further evaluate a potentially clinically significant ECG finding.

Special care must be taken for proper lead placement by qualified personnel. Skin should be clean and dry prior to lead placement. Participants may need to be shaved to ensure proper lead placement. Female participants may need to remove their bra. Participants should be resting in the semirecumbent position for at least 10 minutes prior to each ECG measurement.

8.3.4 *Sexually Transmitted Infections*

8.3.4.1 *HIV Infection*

Participants who have a positive HIV-1/2 screen test while on study intervention will return to the site for a confirmatory HIV-1 RNA PCR test and collection of a viral drug resistance sample, as soon as possible and no later than 14 days after receiving the positive HIV-1/2 screen test result. If HIV-1 infection is confirmed and the HIV-1 RNA PCR results meet the criteria for testing (HIV-1 RNA \geq 200 copies/mL) genotypic and phenotypic viral drug resistance testing will be performed on collected plasma samples (by the central laboratory).

Participants with confirmed HIV-1 infection will be discontinued from study intervention and referred to local medical providers for HIV care and treatment; they should remain in the study and continue to be followed as outlined in the SoA (Section 1.3). No poststudy ART will be provided.

8.3.4.2 *Other STIs*

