8.3.6 HIV Risk Evaluation

At screening and again at Day 1 prior to randomization, a participant's risk status should be evaluated based on Inclusion Criterion #2 (Section 5.1). A participant that does not meet all elements of Inclusion Criterion #2 should not be randomized. After randomization (Day 1), at each treatment and follow-up visit as specified in the SoA (Sections 1.3.1 and 1.3.2), participants will be screened by appropriate study-site personnel for changes in HIV risk behaviors based on the list of questions included in Appendix 8.

Any participant who develops a risk for HIV infection at any time during the study should be brought to the attention of the Sponsor. No further study intervention should be administered from the time the site is made aware of the change in risk status until the Sponsor has provided guidance.

Upon assessment of the increase in risk status, the Sponsor will determine: a) the appropriateness of continuing study intervention and/or b) the necessity to refer the participant for applicable services (eg, substance use, mental health, PrEP).

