Total Blood Volume per Visit in mL (All Participants)	29.2	35	11	0	0	0	20.1	20.1	20.1	20.1	26.1	11	17.5	0	17.5	227.7	29	20.5	
PBMC Substudy Only																			
PBMC sample		32	16	16	16	16	16	16	16	16	32	16	16	16	16	256	16	16	
Venous Microsampling (eg, Mitra [®] /VAMS)		2.6	2.6	2.6	2.6	2.6					2.6	2.6	2.6	2.6	23.4	2.6	2.6		
Hematology				2	2	2							2		8				
TBNK Panel/CD4+ T-cell Count				6	6	6							6		24				
Chemistry				4	4	4							4		16				
Cystatin-C				2	2	2							2		8				

Study Period	Screening	Intervention (Blinded)												Follow-up (Blinded)				HIV Infection Conf	Early Withdrawal From Study
Scheduled Day/Week	Screening	Day 1	Day 2	Week 1 ^a	Week 2 ^a	Week 3 ^a	Week 4	Week 8	Week 12	Week 16	Week 20 EOT ^c	FD 1	FW 4	FW 6 ^a	FW 8	Totals	Unscheduled	Unscheduled	
Additional Blood Volume Collected per Visit in mL (Participants in the PBMC Subset)		34.6	18.6	32.6	32.6	32.6	16	16	16	16	32	18.6	18.6	32.6	18.6	335.4	18.6	18.6	

β-hCG=beta human chorionic gonadotropin; EOT=End of Treatment; FD=follow-up day; FW=follow-up week; HBV=hepatitis B virus; HCV=hepatitis C virus; HIV-1=human immunodeficiency virus type 1; HIV-2=human immunodeficiency virus type 2; INR=International Normalized Ratio; PK=pharmacokinetic(s); PBMC=peripheral blood mononuclear cell; PCR=polymerase chain reaction; POCBP=participant of childbearing potential; PT=prothrombin time; RNA=ribonucleic acid; TBNK=T- and B-Lymphocyte and Natural Killer Cell.

a. Visits at Week 1, Week 2, Week 3, and Follow-up Week 6 are for participants who provide consent to participate in the PBMC Subset only.

b. Not collected if the participant is beyond Follow-up Day 1.

c. If performed as an EOT visit (as per Section 1.3.1), not all samples are required therefore the blood volume is reduced; refer to Section 8.11.3 for additional details.

Table 12 Blood Volumes for Samples Collected From Participants in South Africa

Study Period	Screening	Intervention (Blinded)												Follow-up (Blinded)				HIV Infection Conf	Early Withdrawal From Study
		Day 1	Day 2	Week 1 ^a	Week 2 ^a	Week 3 ^a	Week 4	Week 8	Week 12	Week 16	Week 20 \EOT ^c	FD 1	FW 4	FW 6 ^a	FW 8	Totals			
Scheduled Day/Week	Screening															Unscheduled	Unscheduled		
All Participants																			
HIV Elisa 4th Generation	3.5	3.5						3.5	3.5	3.5	3.5		3.5		3.5	31.5		3.5	
HIV Confirmatory Test (Bio Rad Geenius)																			
HBV/HCV/HIV (Serology)	3.5															3.5			
HCV RNA (only tested if AB+)	3.5															3.5			

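### After a reactive HIV-1/2 screen with a negative differentiation test, Protocol 8.11.4 allows the next monthly dose before the HIV-1 RNA result is known; a one-sentence hold would close this small gap

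*Protocol*

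**What the plan says.** Protocol 8.11.4 splits positive HIV-1/2 screens that occur before the Week 20 dose by the result of the confirmation and differentiation test.

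- **Differentiation negative:** "the participant may continue study intervention while waiting for the results of the HIV-1 RNA PCR test". Once the result is in: "If the HIV-1 RNA PCR test is negative, the participant can continue to take study intervention". If RNA is positive, the participant goes to the EOT visit, follow-up and referral.
- **Differentiation positive:** no more doses are given while RNA is pending, and resuming after a negative RNA needs consultation with the Sponsor.

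The RNA sample is taken at a separate HIV Infection Confirmation visit. Section 8.3.4.1 sets its timing: "as soon as possible and no later than 14 days after receiving the positive HIV-1/2 screen test result".

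Two other rules bear on dosing:

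- **Change in HIV risk (8.3.6):** "No further study intervention should be administered from the time the site is made aware of the change in risk status". The hold lasts until the Sponsor gives guidance.
- **Unconfirmed lymphocyte or CD4+ decrease (7.1):** "Participants should interrupt QM blinded dosing pending confirmatory testing".

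The end of 8.11.4 makes separate provision for participants with repeated screens judged false positive. After a documented decision with the Sponsor, "HIV RNA testing can be performed at each scheduled visits to avoid the participant needing to return for an HIV confirmation visit".

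**The concern.** A reactive screen with a negative differentiation test may be a false positive or an early infection. The protocol accepts both possibilities, because it orders HIV-1 RNA and provides for a positive result. In this branch RNA is the deciding test, yet nothing requires the site to wait for it before dosing.

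If the participant is infected, the extra dose is further exposure to one antiretroviral used alone. The protocol takes a drug-resistance sample at the same visit, and Section 2.2.1 reports an 11-fold loss of potency against M184V/I. Section 2.3 describes direct benefit to these participants as minimal, so little is lost by waiting. The stake is the safety of an individual participant. The safety and PK analyses are unaffected.

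**Working it through.** **1. What the confirmation visit can establish.** Protocol Tables 11 and 12 give 29 mL for this visit. The components are hematology, TBNK, plasma PK, HIV-1 RNA and resistance testing:

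- Table 11: 2 + 6 + 3 + 6 + 12 = 29 mL
- Table 12: 4 + 4 + 3 + 6 + 12 = 29 mL

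Both totals reproduce with no serology tube. This agrees with Section 1.3.2, where the row "HIV-1 and HIV-2 screen" is marked only under Early Withdrawal. At this visit the decision therefore rests on RNA.

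**2. When a dose can precede the RNA result.** Let V be the days from the site receiving the screen result to the confirmation visit (0 to 14, from 8.11.4). Let S be screen turnaround plus RNA turnaround. The documents do not give S, so I assume 4 to 14 days. A dose comes first when the dose interval is shorter than S + V. The shortest intervals come from the Table 4 windows.

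| Dose pair | Interval (days) | S needed when V = 14 |
|---|---|---|
| Nominal spacing | 28 | more than 28 − 14 = 14 |
| Day 1 to Week 4, shortest | 27 − 1 = 26 | more than 26 − 14 = 12 |
| Week 4 to Week 8, shortest | 50 − 31 = 19 | more than 19 − 14 = 5 |
| Later pairs, shortest | 78 − 64 = 14 | more than 14 − 14 = 0 |

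- At S = 4, the gap needs a 14-day interval and V above 10. At 19 days V would have to exceed 15, which is not permitted.
- At S = 14, the gap needs V above 0 at 14 days, above 5 at 19 days and above 12 at 26 days. It cannot occur at 28 days.
- If S were as long as 21 days (7 for the screen, 14 for RNA), it could occur at nominal spacing once V exceeds 28 − 21 = 7.

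**3. Who is already held.** Section 1.3.2 marks the HIV infection risk evaluation, using Appendix 8, at the confirmation visit. Section 1.3.1 marks it at every dosing visit. Any qualifying answer, or a change deemed by the investigator, stops dispensing until the Sponsor is consulted. Only participants without a reported or deemed risk change remain exposed to the gap.

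**4. Expected numbers.** The rates here are assumptions, and full completion is assumed.

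- Screens that precede a further dose (Day 1, Weeks 4, 8, 12 and 16): 350 × 5 = 1,750. At an assumed false-positive rate of 0.1% to 0.5%, this gives 1.75 to 8.75, or about 2 to 9 positive screens.
- Person-time on active drug during dosing: 300 × 20/52 = 115.4 person-years. At an assumed incidence of 0.2 to 1 per 100 person-years, this gives 0.23 to 1.15 infections.
- An affected participant must be infected, differentiation-negative, without a risk change, and dosed before RNA is read. Even at the upper incidence, 1/1.15 = 87% of all infections would have to meet all these conditions to reach one expected case.

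**5. Cost of a hold.** Days from the latest permitted screen to the end of the next dosing window (Table 4):

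- Day 1 to Week 4: 31 − 1 = 30
- Week 4 to Week 8: 64 − 31 = 33
- Later pairs: 92 − 64, 120 − 92 and 148 − 120, each 28

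With S = 14 and V = 14 the result arrives on day 28, at the edge of the tightest windows, so the dose can still be given. A longer wait can mean a skipped dose under 8.1.8.1.

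**The case against.** The strongest reply is that this is a deliberate tiered rule. A second test has already been done and was negative, and when that test is positive the protocol does hold the dose. A reader might infer that the protocol contradicts itself by being stricter for weaker signals in 7.1 and 8.3.6. The documents do not support that. The lymphocyte and CD4+ hold guards against possible drug toxicity before any second test, and the risk hold serves PrEP eligibility and referral. The comparison shows that the protocol tolerates dose holds; it does not show an inconsistency.

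The wording is also permissive. An investigator may withhold the dose, must seek RNA promptly, and under Appendix 2 uses local results when central ones are not available in time for dosing. These points stand and reduce the risk, but none requires a hold in every such case.

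A reader might further infer that the confirmation visit should repeat serology. It is true that none is drawn there and that the RNA test covers HIV-1 only. But Section 1.3.1 already repeats the HIV-1/2 screen at the next dosing visit. A repeat would add a procedure with no stated turnaround and largely duplicate that screen.

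Finally, a reader might infer that a negative RNA on drug is unreliable. Using the P003 half-life of 216 to 291 hours, 34–45% of the triphosphate remains 14 days after a dose and 12–20% at 28 days. Those half-lives come from 10 to 40 mg doses, and the documents give no way to compute a false-negative rate. The same figures show that a hold does not end drug exposure. It avoids only the added dose.

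**Conclusion.** The point holds in a limited form. Section 8.11.4 permits a dose before the deciding RNA result in the differentiation-negative branch, and no other text requires a hold in every such case. The window opens when a late visit or slow turnaround outruns the dose interval, which for S of 4 to 14 days means a shortened interval. The exposed group is early infections without a reported or deemed risk change, and the expected count is well under one. Later scheduled screens would probably still find the infection. These sizes rest on assumed turnaround, false-positive and incidence rates; the interval arithmetic rests on Table 4 alone.

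The documents do not support reading this as a serious safety failure or as a threat to the trial's results. No endpoint, comparison or sample size changes. It is an optional improvement, worth making because it is cheap.

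**What to change.** In 8.11.4, differentiation-negative branch, replace the permission to continue while RNA is pending with: *should receive no further dose until the HIV-1 RNA PCR result is available and reviewed.* The text on what follows a negative or positive RNA stays as it is.

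State also that participants under the documented repeated-false-positive rule at the end of 8.11.4 are exempt. Their RNA is drawn at scheduled visits, so a hold would otherwise disrupt every dose. They can still be dosed before RNA is read, under the decision already documented with the Sponsor.

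No change is needed to the differentiation-positive branch, to Section 1.3.2 or to the blood volumes. The cost is one sentence plus the exemption. Nothing is lost when RNA is back on time. Otherwise an occasional false-positive participant, among an assumed 2 to 9 positive screens in the whole study, has a late dose, or a skipped one if results take longer than about 28 days from the screen.
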